4.1.4 Concomitant Medications/Treatments

Ideally, subjects should not receive other antineoplastic agents for at least 6 weeks post T cells (for purposes of evaluation) however, subjects with progressive disease may receive other therapy if needed at the discretion of their attending physician. If subjects receive other therapy adverse event reporting will cease after the initial 6-week assessments outlined in section 4.2 are completed. These subjects will continue to be monitored after PD according to the Time and Events Table in APPENDIX IV - Abbreviated Follow Up Required After Initiating Alternative Therapy (section 18.4).

If subjects experience PD after the initial 6-week assessment period following the cell infusion has been completed, they should be followed according to the Time and Events Table in APPENDIX IV - Abbreviated Follow Up Required After Initiating Alternative Therapy(section 18.4).

Confidential
Page 55 of 154

4.2 Time & Events Table

Table 4Time and Events Table

	S	Screening ¹			Follow-up										
Study Assessments	Pre- procurem ent		Pre-infusion of ATLCAR. CD30 cells	Wk 0 D1 ¹	Wk 1 D1 ¹	Wk 2 D1 ¹	(Opti onal) Wk 3 D1 ¹	Wk 4 D1 ¹	Wk 6 D1 ¹	Mth 3 D1 ¹	Mth 6 D1 ¹	Mth 9 D1 ¹	Mth 12 D1 ¹	Every 6mths x 4 yrs ¹	Yearly ^{1,17}
History ³	X		Х		Х	Х	Х	Х	Х	Х	Х	Х	Х		Х
Physical exam			Х		Х	Х	Х	Х	Х	Х	Х	Х	Х		X^{1*}
Check Eligibility	X	ASC	X												
Performance status ¹	X	ASCT AS	Х			Х				Х	Х	Х	Х		
Pregnancy test ²	X	PER	Х												
PFTs and EF ⁴	X	STA													
Pulse oximetry		ND	Х												
CBC with diff ^{5, 19}	X ⁵	STANDARD	Х		Х	Х	Х	Х	Х	Х	Х	Х	Х		
Virus testing ⁶	X ⁶	OF C∤													
Procurement of cells	After screening 7	CARE													
Complete metabolic panel ⁷	X ⁷ *		Х		Х	Х	Х	Х	Х	X	Х	Х	X		
Tumor Imaging ⁹	X								Х		Х		Х	X9	
Thyroid function ¹⁰			Х							Х			Х		

LCCC1524-ATL

Administration of T lymphocytes Expressing the CD30 Chimeric Antigen Receptor (CAR) for Prevention of Relapse of CD30+ Lymphomas after High Dose Therapy and Autologous Stem Transplantation (ATLAS)

Confidential

ATLCAR.CD30

Page 56 of 154

Correlative Samples ¹¹			Х	X	X	Х	Х	X	X	Х	Х	X	Х	X ¹¹	X ^{11,17}
HAMA testing ¹²			X ¹²						X ¹²						
Toxicity ¹³		-	Х	X	X	X	X	X	X						
СоА			X ¹⁴												
Infusion of ATL CAR.CD30				X ¹⁵											
PRO Questionnaires (optional) ¹⁶	X		Х		X	Х	Х	X	X	Х	Х	Х	Х	X	X
Tissue Studies		See Section 7.5.7													

Key to Time and Events Table Footnotes

- Screening includes tests to confirm eligibility for both procurement and treatment; NOTE: some pre-infusion screening tests may not be performed until the day of infusion. A window of +/-3 days will apply to all study visits for the first 8 weeks unless otherwise noted below. A window of +/-10 days will apply to every 3 months study visits, and a window of +/-30 days will apply to visits separated by ≥ 6 months. Yearly follow-up visits during long-term follow-up for a total of 15 years. *An annual physical exam will be required ONLY for the first 5 years of follow up. NOTE: Follow-up visits for month 3 and beyond can be conducted locally (i.e., by local health care provider, local oncologist, etc.). The study team would continue to contact the subjects at the long-term follow-up points and request they visit their local healthcare provider to complete the follow-up test and assessments, where applicable. The study team would collect clinical information, tests and assessments results, other clinical observations from the subject's medical record and their local health care provider.
- 2. Serum pregnancy testing will be done in female subjects of childbearing potential within 72 hours prior to procurement and repeated 72 hours prior to infusion.
- 3. Medical history must include collecting the following information: 1. New malignancy(ies) 2. New incidence or exacerbation of pre-existing neurologic disorder 3. New incidence or exacerbation of a prior rheumatologic or other autoimmune disorder 4. New incidence of a hematologic disorder and 5. New incidence of infection (potentially product related).
- 4. PFTs = pulmonary function tests and includes forced expiratory volume in 1 second (FEV1), forced vital capacity (FVC) and diffusing capacity (DLCO); EF=ejection fraction evaluated via MUGA or ECHO. These will be evaluated within 3 months prior to transplant.
- 5. CBC includes complete blood count with diff and platelets. *NOTE: Preprocurement, only Hg is necessary, and if a serum Hg has already been performed within 7 days of procurement as part of SOC pre-transplant work-up, it does not need to be repeated. Prior to ATLCAR.CD30 treatment, CBC with diff and platelets must be performed within 24 hours prior to infusion. CBC with diff and platelets performed as needed on D1/Week 3.
- 6. HIV, HBV, HCV testing required for confirmation that no active infection exists; results can be pending at the time of cell procurement; only those samples confirming lack of active infection will be used to generate transduced cells. Virus testing may be performed up to 30 days prior to procurement.

- 7. See section 8.2, procurement happens after pre-procurement screening and prior to ASCT. Procurement may occur prior to or after PBSC mobilization. If procurement occurs after PBSC mobilization, it must occur at least 7 days after ending use of G-CSF
- 8. Complete Metabolic Panel (CMP): includes BUN, creatinine, Na, K, Cl, CO2, glucose, calcium, albumin, total protein, total bilirubin, ALT, AST, and alkaline phosphatase. NOTE: *Pre-procurement, only creatinine, bilirubin, and AST is necessary, and if these tests have already been performed within 7 days of procurement as part of SOC pre-transplant work-up (i.e. as part of CMP), they do not need to be repeated. Prior to ATLCAR.CD30 treatment, a CMP must be performed within 24 hours prior to infusion. CMP performed as needed on D1/Week 3.
- 9. To assess disease status, imaging will be performed at baseline (within 60 days prior to ASCT) and at 6-8 weeks following the infusion. The choice of imaging will depend on what studies have been most informative in following the subject's disease (i.e., PET, CT scans, MRI, nuclear imaging). In subjects who do not have documented disease progression at the 6 weeks scan, another scan will occur at 6 months, 12 months, 18 months and 24 months (with a +/- 1 month window), until documentation of disease progression. If imaging studies are performed at other times after treatment on this study; that data will be collected, and information gained will be used for this study.

Response assessment for subjects with cutaneous T cell lymphoma

- a. Will be performed at the same time point outlined above in the Time and Events Table and by the few exceptions outlined in section 7.1.1.
- b. Notable differences in the follow up for these subjects are outlined in section 7.1.1 based on consensus guidelines.
- c. Consult with a dermatologist will be required within 14 days prior to transplant.
 - 10. Thyroid function (T3, Free T4 and TSH) will be monitored in view of changes seen in subjects receiving CD30 antibody.
 - 11. Correlative analysis will include the following. Correlative blood sample collection will cease if the samples are no longer required for persistence and function or clonality analysis.
- a. **Persistence and Function:** The analyses will be used to monitor persistence and function (if applicable) in peripheral blood and will include immunophenotyping as well as quantitative polymerase chain reaction (qPCR) to detect transgene persistence and

functional assays such as in vitro reactivation of PBMCs in subjects for whom the appropriate reagents are available. Quantitative real-time PCR to detect the transgenes will be collected pre-lymphodepletion, pre-dosing (approximately 19 mL of blood), at 3 - 4 hours post infusion (approximately 16 mL of blood), 1, 2-, 3-, 4- and 6-weeks visits post each T-cell infusion and then at the 3-, 6-, 9-, and 12-months visits. Persistence and function will be continued for up to one-year post-CAR T cell infusion. If a transgene copy number is > 500 copies/µg DNA, then samples to determine transgene copy number is < 500 copies/µg DNA at which time samples will then be collected yearly for up to a total of 15 years. If transgene is no longer detectable by PCR after 1-year post-final CAR T infusion, then collection for function and persistence will discontinue. See Section 7.5.1 and the Laboratory Manual for the amount of blood collected/type of tube used for all of the correlative studies.

- b. **Clonality:** If the transgene is detected at > 0.5% either flow cytometry (if feasible) or by qPCR at the 6-month sample collection timepoint, then PCR to detect retroviral integrant clonality and integrant locus will be performed. This analysis will continue every 6 months until detection is < 0.5% for up to 5 years. After this time, it will be collected annually. If the level of detection is < 0.5% at 6-months, samples will be collected annually and may be archived. Samples will no longer be collected if detection is < 0.5% for more than 1 consecutive testing period. See Section 7.5.3.
- c. **RCR:** For replication competent retrovirus (RCR) testing, subject blood samples will be collected and stored pre-infusion. The pre-infusion sample will only be tested if the subject develops a long-term gene therapy side effect as described in Section 7.5.2. Additional samples for RCR testing will only be collected and subsequently analyzed in the event that the subject develops a long-term gene therapy side effect as described in Section 7.5.2.
- d. Cytokine Testing: Serum collected before and 3-4 hours after infusion for cytokine testing.
 - 12. Serum from blood drawn for functional studies at baseline and week 6 will be stored for measurement of human anti-mouse antibodies (HAMA). These studies will be performed in the event of a suspected immunologic reaction. See section 7.5.4 for additional details.
 - 13. Data on all adverse experiences/toxicities per CTCAE v4.0 regardless of seriousness must be collected for documentation purposes only for 6 weeks after dosing of the study drug/biologic. Adverse event data collection will cease in subjects that receive any other hemopoietic cell product or receive therapy for relapse of their primary malignancy. Data on disease status will continue to be collected as appropriate.

- a. If CRS signs and symptoms occur (see APPENDIX VIII- CRS Toxicity Grading Scale and Management Guidelines), a serum sample (~1 mL) for IL-6 analysis and 20 mL of blood should be collected before instituting treatment for CRS. Subsequent 20 mL blood samples should be collected once a day for the first 3 days. At the discretion of the sponsor, a daily sample may be requested for an additional 4 days. See section 7.5.6 for additional details.
- b. Serum (~1 mL) and 20 mL of blood should also be collected in the event of serious toxicities that develop that require hospitalization. Subsequent 20 mL blood samples should be collected once a day for the first 3 days. At the discretion of the sponsor, a daily sample may be requested for an additional 4 days. See section 7.5.6 for additional details.
- c. An additional blood sample of approximately 20 mL may be collected if any subject develops an AE or event of clinical significance that is thought to be at least possibly related to the CAR T cells.
 - 14. CoA generated at completion of required studies for production/QA of cells.
 - 15. ATLCAR.CD30 cells infused after evidence of hematologic recovery post ASCT, see section 4.1.2 for definition of recovery. This will generally occur between 14 and 20 days following infusion of autologous stem cells following high-dose chemotherapy. All subjects will receive their ATLCAR.CD30 infusion at the lead site, the University of North Carolina, Chapel Hill.
 - 16. Patient reported outcomes (PRO) will be measured by the PROMIS Global Health and Physical Function questionnaires and selected items from the NCI PRO-CTCAE (see section 7.6 and APPENDIX V - Patient Reported Outcomes Surveys) (optional). PRO questionnaires will only be offered to adult study participants. PRO questionnaires will first be given at time of screening consent. On the day of infusion, subjects will fill out questionnaires prior to infusion. These questionnaires are optional and may not be given to all subjects.
 - 17. Long Term Follow Up: If a subject develops a delayed adverse event that is related to the trial drug, then more frequent (2-4 times per year) clinical observation may be indicated. Appropriate follow up will be conducted based on a particular subject's prior test results. The investigator will determine the additional testing and sample collection that is needed. New malignancies and delayed adverse events will be recorded during long term follow-up.

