7.4 Long Term Follow-Up

Quantitative real-time PCR to detect transgene copy numbers will be collected preinfusion, 3-4 hours post infusion, 1, 2, 3, 4 and 6 weeks post- T cell infusion, 3, 6, 9, and 12 months post- T cell infusion and then yearly for a total of 15 years. If transgene copy number is >1000 copies/1µg DNA, then samples to determine transgene copy numbers will be collected every 6 months after the first year until transgene copy number is <1000 copies/1µg DNA at which time samples will then be collected yearly for a total of 15 years.

If at 6 months post- T cell infusion, transgene is detected at >0.5% by flow cytometry then PCR to detect retroviral integrant clonality and integrant locus will be performed and will continue every 6 months until detection is <0.5%. Samples will then be collected annually and may be archived for a total of 15 years. If the level of detection is less than 0.5%, samples will be collected annually and may be archived. Follow up will continue for 15 years.

If a subject develops a delayed adverse event that is related to the trial drug, then more frequent (2-4 times per year) clinical observation may be indicated. Appropriate follow up will be conducted based on a particular subject's prior test results. The investigator will determine the additional testing and sample collection that is needed. New malignancies and delayed adverse events will be recorded during long term follow-up.

Regarding annual genetic analysis through year 15, see Section 7.5.5.

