7.5 Correlative Studies: Tests of Function, Persistence and Safety

The following investigations will be used to monitor function and persistence in peripheral blood and safety of transduced T-cells at time-points indicated in the Time and Events Table. A maximum of the lesser of 50 mL or 2 mL/kg of body weight of blood will be drawn on any one day for these assays. If a subject's hemoglobin is less than 8.0 g/dL at any of the evaluation times, the amount of blood drawn for the evaluation will be reduced and may be obtained over more than one venipuncture, if necessary. If there is insufficient blood, samples archived for RCR testing if needed, and Quantitative real-time PCR, will be the first priorities. Note: the studies are not necessarily performed at the time of blood collection. Correlative blood sample collection will cease if the samples are no longer required for persistence and function or clonality analysis.

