11.3.3 Analysis of Expansion and Persistence of Transduced T Cells

The frequency of T cells transduced with the vector (T cells expressing will be summarized at pre and post-infusion time points using mean \pm SD, medians and ranges to evaluate their expansion and persistence. Changes in each of these T cells from pre-infusion to each time point of post-infusion will be assessed and compared using paired t-tests, or when appropriate, the Wilcoxon signed ranks test. Paired comparisons of these T cells within a subject at each time point will also be performed. These analyses will be performed in the overall subject group.

Plots of growth curves will be generated to graphically illustrate patterns of T-cell expansion. Plots will be generated to depict patterns of survival and expansion of T cells for each of the two vectors. Longitudinal modeling techniques such as the random coefficient mixed model will be employed to model each of the repeatedly-measured T cells. These models account for variation in individual-level intercepts and slopes over the follow-up time. Thus, we will be able to model proliferation of T cells over time and estimate the magnitude of expansion or decline of T cells. We will include dose level as an independent variable in the model to account for different doses received by subjects.

Alternative strategies to analyze these outcomes include calculation of area under the curve over time for T cell frequencies or piecewise longitudinal models based on apparent trends from plots of growth curves. Despite the small subject numbers, a datadense study will be generated due to the repeat measurements on proliferation, immune function, etc. on each subject. The modeling strategies proposed here are amenable to these types of data but will however be considered exploratory and interpreted with caution due to limited study power.

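### After year 1, persistence sampling depends on the subject's own transgene result, and Section 11.3.3 has no rule for subjects whose sampling stopped, so later available-data summaries could overstate persistence

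*Combined protocol and SAP*

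**What the plan says.** Persistence by quantitative PCR and flow cytometry is a secondary endpoint (Section 3.2.3).

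**Sampling in year 1.** Footnote 11a in Section 4.2 schedules PCR samples around the infusion, over the first 6 weeks, "and then at the 3-, 6-, 9-, and 12-months visits". No result-dependent stop applies in this period.

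**Sampling after year 1.** Footnote 11a then says that if PCR no longer detects the transgene beyond 1 year from the last infusion, "then collection for function and persistence will discontinue". Appendix IV has the same rule for subjects who have started alternative therapy. Section 7.5 is consistent with it: "Correlative blood sample collection will cease if the samples are no longer required for persistence and function or clonality analysis". Appendix IV also makes 6-monthly samples after year 1 conditional on more than 500 copies/µg DNA, with yearly samples below that. Footnote 11a uses the same threshold, though its sentence is incomplete in the text available.

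**A different schedule.** Section 7.4 has PCR at "12 months post- T cell infusion and then yearly for a total of 15 years". It contains no stop for an undetectable result, and its threshold for 6-monthly samples is 1000 copies.

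**Analysis.** Under Section 11.3.3, the frequency of transduced T cells "will be summarized at pre and post-infusion time points using mean" and SD, with "medians and ranges to evaluate their expansion and persistence". It adds: "Changes in each of these T cells from pre-infusion to each time point of post-infusion will be assessed and compared using paired t-tests", or a signed-rank test where appropriate. The analyses are for the overall subject group, and a random-coefficient mixed model is also planned. The section names no last visit, no value for results below the detection limit, and no treatment of subjects whose sampling was stopped.

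**The concern.** Under footnote 11a, whether a subject has a persistence sample after year 1 is decided by the quantity being measured. Subjects who have lost the cells leave the sampling schedule, and those who still have them remain. A mean or median over the samples in hand at a later visit then describes a group selected for persistence.

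The 6-monthly samples add a second selection. Between yearly visits only subjects above the copy-number threshold are due for a sample, so a subject with detectable but low copy number is also absent.

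At stake is the late description of a named secondary endpoint. If stopped subjects are simply absent from the calculation, the report could show sustained persistence when most infused subjects had lost the cells. With 12 to 18 subjects expected (Section 11.2), a few stopped subjects are enough to move a mean materially.

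**Working it through.** The documents state no expected persistence rate, so there is no planned figure to reproduce. The rates below are assumptions, shown over a range.

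**Inputs from the documents.** Stopping rule: footnote 11a and Appendix IV. Sample size: 12 to 18 (Section 11.2). The Study Summary says 40, but the ratios below do not depend on it. Assay sensitivity: one transduced cell in 50,000 mononuclear cells (Section 1.6), that is 1/50,000 = 0.002%.

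**Step 1: through month 12.** Every subject is scheduled for sampling whatever the result. The ratio of sampled-only to all-subject mean is 1.0.

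**Step 2: after month 12, stopped subjects at zero.** Let N subjects be alive and in follow-up, a share u of them stopped with true level about zero, and S the sum of the levels of the others. The sampled-only mean is S/[N(1-u)] and the all-subject mean is S/N. Their ratio is 1/(1-u), whatever the distribution of levels among those still sampled.

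- u = 30%: 1/0.70 = 1.43
- u = 50%: 1/0.50 = 2.00
- u = 70%: 1/0.30 = 3.33

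**Step 3: stopped subjects at the detection limit.** With sampled mean m, the ratio is m/[(1-u)m + 0.002u], in percent. At u = 50%:

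- m = 0.01%: 0.01/(0.005 + 0.001) = 1.67
- m = 0.5%: 0.5/(0.25 + 0.001) = 1.99

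The bias stays upward and is only modestly smaller.

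**Step 4: following the rule over yearly visits.** Assume a share p is undetectable at month 12, and a share h of those still detectable becomes undetectable each year after that. A subject's first undetectable sample is taken and counted; later ones are not taken. The share sampled at year y (from 2 on) is (1-p)(1-h)^(y-2), and the mean ratio is its reciprocal.

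| p / h | Year 2 ratio | Year 5 share sampled | Year 5 ratio |
|---|---|---|---|
| 20% / 10% | 1/0.80 = 1.25 | 0.80 × 0.90³ = 0.583 | 1.71 |
| 50% / 20% | 1/0.50 = 2.0 | 0.50 × 0.80³ = 0.256 | 3.9 |
| 70% / 30% | 1/0.30 = 3.3 | 0.30 × 0.70³ = 0.103 | about 10 |

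A simulation with 18 subjects and 20,000 replicates gave the same ratios. In the middle case about 18 × 0.256 = 4.6 subjects are sampled at year 5. Of those, 80% are detectable, against 0.50 × 0.80⁴ = 20% of all subjects.

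**Step 5: medians.** The factor 1/(1-u) applies to means. If more than half of the subjects have stopped, the all-subject median is below the detection limit, while the sampled-only median can still be a positive value.

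**Step 6: if Section 7.4 governs.** Every subject is due for a yearly sample, so the ratio at yearly visits is 1.0. Half-year visits remain selective, because Section 7.4 also makes them conditional on copy number.

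**The case against.** The strongest reply is that the plan never commits to the biased summary. Section 11.3.3 names no visit after month 12, and footnote 11a describes persistence and function studies as running for up to one year, so the summaries may be meant for year 1 only. The section also refers to the overall subject group and nowhere says that stopped subjects are left out. Their last result is known to be undetectable, so counting them as zero fits the text. This stands in part: the overstatement is a likely default of an available-data summary and not a stated plan. But the paired comparisons are planned for each post-infusion time point without an end date, and sampling can run to year 15, so the text does not exclude the late summaries either.

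A reader might infer that from month 18 the data hold only subjects whose cells persisted. The documents do not support that. A subject detectable at one visit is sampled at the next due visit and can contribute a first undetectable value there. Nor is the stop settled: Section 7.4, also current text, does not contain it.

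The mixed model is less exposed than the raw summaries. Stopping depends on an observed value, so a correctly specified likelihood analysis can accommodate it, although linear slopes may fit poorly with values at the detection limit. The means, medians, ranges and paired tests have no such protection.

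Finally, this is a mainly descriptive secondary endpoint in a small phase I trial, and the plan already calls its modelling exploratory. That limits the consequence but does not supply the missing rule.

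**Conclusion.** The concern holds in a conditional form. If footnote 11a and Appendix IV govern, and if summaries after month 12 use only the samples taken, persistence is overstated by 1/(1-u): 1.4, 2.0 and 3.3 times for an assumed u of 30%, 50% and 70%. The direction is always upward. The size rests on the assumed share stopped, on stopped subjects staying at about zero without later reappearance, and on their being omitted.

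Summaries through month 12 are unaffected, as are dose escalation and the MTD. If Section 7.4 governs, the bias is absent at yearly visits; selection by copy number at half-year visits remains under either text. It would go too far to say that the plan excludes stopped subjects or that its persistence results will be wrong. The documents show a sampling rule that depends on the outcome, with no matching analysis rule. That should be corrected before late persistence is reported.

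**What to change.** 1. Reconcile Section 4.2 (footnote 11a), Section 7.4 and Appendix IV on whether sampling stops for an undetectable transgene, and on the copy-number threshold (500 or 1000).
2. In Section 11.3.3, keep subjects whose sampling stopped for undetectable transgene in later yearly summaries as below the detection limit while they are alive and in follow-up. Use 0 in the main summary and the detection limit as a sensitivity value.
3. At each yearly visit, report the proportion detectable among infused subjects alive and in follow-up, with that same denominator throughout.
4. Limit all-subject summaries after year 1 to yearly visits, since subjects below the copy threshold are not due for half-year samples.
5. If time to loss of detectability is reported, label it supportive, state how deaths are handled, and count a loss only when no later detectable result follows.

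The cost is a few sentences of analysis text and no new blood samples. Late persistence figures will look less favourable than sampled-only figures would.
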